## 3.2 Study Outcome Measures

### 3.2.1 Primary Outcome Measures:

The efficacy of azithromycin versus placebo on Day 5 will be based on clinical improvement.

- Clinical improvement will be defined as fulfillment of **all** the following criteria:
  1. Improvement in at least two symptoms present at enrollment (i.e., cough, sputum production, chest pain, or difficulty breathing) or one symptom and at least one vital sign abnormality present at enrollment. For symptoms, at least a one-step improvement (e.g., improvement from moderate to mild cough) will be considered a clinical improvement (Table 1). For vital sign abnormalities, normalization of the

presenting abnormal vital sign will be considered a clinical improvement. Qualifying vital signs and their normal values will include the following:

- temperature (<37.8°C or 100.0°F),
  - pulse (<90 bpm),
  - respiratory rate (≤20 breaths per minute),
2. Absence of deterioration in any qualifying symptom (i.e., cough, sputum production, chest pain, or difficulty breathing); or new vital sign abnormality not present at enrollment. For symptoms, at least a one-step deterioration (e.g. worsening from mild to moderate cough) will be considered clinical deterioration (Table 1).
  3. Absence of fever in the day preceding or at the Day 5 Visit (fever is defined as ≥37.8 °C or 100.0 °F, measured anywhere on the body).
  4. No medically attended visit to an ambulatory medical facility (e.g., ED, outpatient clinic, urgent care center) or hospitalization for persistent or worsening LRTI at any time after randomization (persistent or worsening LRTI is defined as receipt of a non-study antibiotic [parenteral or oral] treatment for LRTI or its complication).  
**Note:** receipt of a non-study antibiotic after study Day 5 will not be regarded as satisfying this definition if it is related to a new non-respiratory process that is unrelated to the prior diagnosis of LRTI

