**Table 3. Solicited Adverse Events for RADAR-DOOR ranking**

	Mild	Moderate	Severe
Abdominal pain	Mild or intermittent and does not interfere with daily activity	Moderate or persistent and interferes with daily activity but did not necessitate a medical visit or absenteeism	Prevents daily activity and resulted in medical visit or absenteeism
Vomiting	1 episode/day	2-3 episodes/day	≥4 episodes/day
Diarrhea	Looser than normal stools occurring 3-6 times/day	Looser than normal stools >6 times/day	Bloody diarrhea or diarrhea that requires clinical evaluation, laboratory testing, or hospitalization
Allergic reaction	New localized rash or itching without rash	New diffuse rash covering multiple areas of the body	New rash requiring clinical visit
Candidiasis	Mild mucocutaneous candidiasis, with no treatment	Moderate mucocutaneous candidiasis, requiring topical or other over-the-counter treatment	Severe mucocutaneous candidiasis; requires urgent clinical evaluation, intravenous treatment, or hospitalization

9. Proportion of subjects reporting solicited adverse events from Day 1 to Day 5 in each treatment group

10. Proportion of subjects reporting one or more hospitalization or visits to an ED, outpatient clinic, or urgent care center (after randomization) for worsening or persistent LRTI from Day 1 through Day 5 in each treatment group

11. The proportion of subjects exhibiting improvement in at least two presenting signs or symptoms at Day 5 in each treatment group
12. The proportion of subjects exhibiting worsening or deterioration in at least one or more symptoms at Day 5 in each treatment group. The proportion of subjects with a new occurrence of a vital sign abnormality at Day 5 in each treatment group.

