### **7.3.4 Visit # 5 Final Visit (Day 28 ± 2 days)**

Study subjects will be evaluated on Day 28 via telephone. Secondary outcome measures will be assessed at this follow up. Study staff will complete the following procedures:

- Assessment of clinical improvement including:
  - Review and collection of temperature
  - Assessment and grading of LRTI symptoms
  - Occurrence of any medically attended visits
  - Receipt of any non-study systemic antibiotics
- Assess and record any UADEs

If the subject develops signs or symptoms of pneumonia (including fever, increased work of breathing, or increased/worsening cough) or develops a severe solicited event, the subject will be referred to his/her primary care provider or local urgent care center/ED. Study staff will assist in facilitating the follow up appointment. The study staff will share all pertinent information

related to the study with the treating clinician including treatment arm assignment if clinically indicated as determined by the treating clinician and the study's site investigator.

The study staff will also review any new or changed con-commitment medications with the subject. A review of the medical record will also be done to recording results of clinical laboratory evaluations as specified in Section 8.2.1.

The exact date of the follow-up visit will be documented throughout the study.

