6.5.1.3. Absence of Fever at D5V

Absence of fever at D5V is defined as absence of fever in the day preceding or at the day of D5V. If the subject had subjective fever or a temperature of $\geq 100.0^{\circ}\text{F}$ reported on the LRT form for Visit 3 (i.e. $\text{LRTTMPF} \geq 100.0^{\circ}\text{F}$ or $\text{LRTFEVYN} = \text{Yes}$), then the subject will be analyzed as having fever at D5V. Similarly, if the subject had subjective fever or a temperature of $\geq 100.0^{\circ}\text{F}$ as reported on the LRS form for the date of the D5V or the day before or if the temperature from the vital sign form (VS1) for Visit 3 is $\geq 100.0^{\circ}\text{F}$, then the subject will also be analyzed as having fever at D5V. If none of the temperature or fever information is available, then absence of fever at D5V is missing. If at least some of that temperature information is available, but none of it indicates objective or subjective fever then the subject has absence of fever at D5V.

6.5.1.4. No Medically Attended Visit or Hospitalization for Persisting or Worsening LRTI at Any Time Post Randomization at D5V

No Medically Attended Visit (MAV) to an ambulatory medical facility (e.g., ED, outpatient clinic, urgent care center) or hospitalization for persistent or worsening LRTI at any time after randomization (persistent or worsening LRTI is defined as receipt of a non-study antibiotic [parenteral or oral] treatment for LRTI or its complication). Note that receipt of a non-study antibiotic after D5V study day will not be regarded as satisfying this definition if it is related to a new non-respiratory process that is unrelated to the prior diagnosis of LRTI. Medically Attended visit information will be recorded on the MAV form.

- If MAVWSCP = ‘Y’ and (MAVABRX = ‘Y’ and (MAVA1RTI = ‘Y’ or MAVA2RTI = ‘Y’ or MAVA3RTI = ‘Y’)), then MAV or Hospitalization for persistent or worsening LRTI at D5V is present.
- If MAVBRX=N or (MAVABRX = ‘Y’ and (MAVA1RTI != ‘Y’ and MAVA2RTI != ‘Y’ and MAVA3RTI != ‘Y’)), then MAV or Hospitalization for persistent or worsening LRTI at D5V is absent.
- If a subject did not complete D5V and had no MAV submitted, then MAV or Hospitalization for persistent or worsening LRTI at D5V is missing.
- Otherwise, if a subject completed D5V but had no MAV submitted then MAV or Hospitalization for persistent or worsening LRTI at D5V is absent.

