6.5.2.2. Absence of Deterioration in Any Qualifying Symptoms at D11V or D28V

Clinical deterioration at D11V or D28V is defined as the deterioration in any qualifying symptoms (i.e., cough, sputum production, chest pain, difficulty breathing, or fever). For symptoms other than fever, clinical deterioration will be determined as the presence of at-least one step deterioration (worsening from mild to moderate) in any qualifying symptom regardless whether the symptom was present at enrollment or not. If at least one of the symptoms has a missing value at D11V or D28V and none of the observed parameters deteriorated, absence of deterioration will be missing at the corresponding visit. If none of the observed symptoms deteriorated and none of them had a missing value, then there is absence of deterioration. If at least one observed symptom deteriorated at study day 11, then there is no absence of deterioration at D11V regardless of whether any parameter has a missing value. Similarly, if at least one observed symptom deteriorated at D28V, then there is no absence of deterioration at D28V regardless of whether any parameter has a missing value.

6.5.2.3. No Medically Attended Visit or Hospitalization for Persistent or Worsening LRTI at Any Time Post Randomization at D11V and D28V

No Medically Attended Visit (MAV) to an ambulatory medical facility (e.g., ED, outpatient clinic, urgent care center) or hospitalization for persistent or worsening LRTI at any time after randomization (persistent or worsening LRTI is defined as receipt of a non-study antibiotic [parenteral or oral] treatment for LRTI or its complication). Note that receipt of a non-study antibiotic after D11V study day will not be regarded as satisfying this definition if it is related to a new non-respiratory process that is unrelated to the prior diagnosis of LRTI. Medically Attended visit information will be recorded on the MAV form. No MAV or hospitalization for persistent or worsening LRTI will then be derived as follows:

- If MAVWSCP = 'Y' and (MAVABRX = 'Y' and (MAVA1RTI = 'Y' or MAVA2RTI = 'Y' or MAVA3RTI = 'Y')), then MAV or Hospitalization for persistent or worsening LRTI at D11V is present.
- If MAVBRX='N' or (MAVABRX = 'Y' and (MAVA1RTI ^= 'Y' and MAVA2RTI ^= 'Y' and MAVA3RTI ^= 'Y')), then MAV or Hospitalization for persistent or worsening LRTI at D11V is absent.

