- If a subject did not complete D11V and had no MAV submitted, then MAV or Hospitalization for persistent or worsening LRTI at D11V is missing.
- Otherwise, if a subject completed D11V but had no MAV submitted then MAV or Hospitalization for persistent or worsening LRTI at D11V is absent.

Similar derivations will be used for D28V by replacing D11V by D28V.

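### Criterion 4 of the Day 5 primary endpoint and the SAP rule that derives it set no closing date, so read literally a medically attended LRTI visit after the Day 5 Visit makes a subject a Day 5 failure

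*SAP*

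**What the plan says.** Protocol 3.2.1, criterion 4, repeated in SAP 3.3.2, requires that there be no visit to an ambulatory facility "or hospitalization for persistent or worsening LRTI at any time after randomization". Persistent or worsening LRTI means receipt of a non-study antibiotic for LRTI or its complication. The only statement about later events is an exemption. In the SAP's wording (6.5.1.4), a non-study "antibiotic after D5V study day will not be regarded as satisfying this definition if it is related to a new non-respiratory process". A later antibiotic for LRTI is not exempted.

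SAP 6.5.1.4 turns this into a rule on form variables. If MAVWSCP and MAVABRX are Y and any of MAVA1RTI to MAVA3RTI is Y, "then MAV or Hospitalization for persistent or worsening LRTI at D5V is present". No visit date or study day enters. SAP 6.5.2.3 repeats the same conditions ("then MAV or Hospitalization for persistent or worsening LRTI at D11V is present") and then says "Similar derivations will be used for D28V by replacing D11V by D28V".

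Collection continues to the last contact: Protocol 7.3.4 lists "Occurrence of any medically attended visits" at Visit 5, which SAP 3.3.1 places on Days 26 to 30.

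Other parts of the plan are limited in time:

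- Protocol 11.1 defines the hypothesis by the probability of improvement at Day 5.
- Protocol 3.2.2, item 10, counts visits "for worsening or persistent LRTI from Day 1 through Day 5 in each treatment group". Protocol 3.2.3, item 4, does the same through Day 11.
- SAP 6.5.5 stops the antibiotic-day count at the study day of each visit.
- SAP 8.3.10.3.1 uses only the visits of the day being scored.

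**The concern.** An endpoint named for Day 5 should be settled by what has happened up to the Day 5 Visit. As written, it can be overturned by a prescription about three weeks later. A subject with a qualifying visit on any day is marked *present* at every assessment, so the Day 5 and Day 11 results partly measure relapse over the whole follow-up.

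The derived outcomes inherit this. The ordinal clinical outcome in SAP 6.5.4 uses clinical improvement together with undated visit and hospitalization terms. In the DOOR score that outcome is combined with an antibiotic count that is dated. The longitudinal count of improvements in SAP 8.3.10.2 is meant to show a pattern over time, yet one late visit can set it to zero.

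For a non-inferiority conclusion, failures added after Day 5 can dilute a true difference between the arms or shift the estimate in either direction.

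**Working it through.** **1. The rule applied literally.** Take a subject with one qualifying LRTI-antibiotic visit, with the Day 5, 11 and 28 Visits held on Days 5, 11 and 28. Flags are in the order D5V / D11V / D28V.

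| Day of visit | SAP rule as written | Limited to the visit's study day |
|---|---|---|
| 4 | present / present / present | present / present / present |
| 9 | present / present / present | absent / present / present |
| 20 | present / present / present | absent / absent / present |
| 27 | present / present / present | absent / absent / present |

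The D28V column does not change. If the Day 5 Visit was missed and the only qualifying visit is late, the written rule returns *present*, an observed failure of the criterion. A dated rule returns *missing*.

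**2. Effect inside one DOOR score.** SAP 6.5.6 scores a subject as outcome category + antibiotic days/100. Take a placebo subject who improved by Day 5 with no solicited events and no antibiotic, and who is given an LRTI antibiotic at a clinic on Day 20.

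- Dated rule: 1 + 0/100 = 1.00.
- Written rule: 6 + 0/100 = 6.00. The visit counts, but the antibiotic it produced does not.

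**3. Inputs for the size.** From Protocol 11.2 and SAP 6.6: p = 57.6% in each arm, margin 12.5 points, two-sided 95% interval, 280 per arm in ATP-5. Let q be the share of Day 5 improvers with a qualifying visit after the Day 5 Visit. The documents do not give q; I assume 0 to 10%.

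The rate recorded in an arm is p(1 − q). With P for placebo, A for azithromycin and n per arm:

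- SE = √{[P(1 − P) + A(1 − A)]/n}
- probability of concluding non-inferiority = Φ[(0.125 + P − A − c/n)/SE − 1.96], with c = 1 for the continuity correction and c = 0 without.

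**4. The plan's own figures.** 560/(1 − 0.169) = 673.9, so 674 reproduces. At q = 0 and 280 per arm, SE = 0.04177 and power is Φ[(0.125 − 0.00357)/0.04177 − 1.96] = 82.8% with the correction, against 80% stated (262 per arm would give 80%). That gap is separate from this point; 82.8% is simply the baseline below.

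**5. True rates equal at 57.6%, 280 per arm, c = 1.**

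| q placebo / azithromycin | Recorded rates | Shift (points) | Power |
|---|---|---|---|
| 0 / 0 | 57.6% / 57.6% | 0 | 82.8% |
| 2% / 2% | 56.4% / 56.4% | 0 | 82.6% |
| 5% / 5% | 54.7% / 54.7% | 0 | 82.3% |
| 10% / 10% | 51.8% / 51.8% | 0 | 82.0% |
| 5% / 2% | 54.7% / 56.4% | −1.7 | 69.9% |
| 10% / 5% | 51.8% / 54.7% | −2.9 | 59.4% |
| 2% / 5% | 56.4% / 54.7% | +1.7 | 91.0% |

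**6. True difference at the margin (45.1% against 57.6%), 280 per arm, c = 0.**

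- q = 0: difference −12.5, one-sided error 2.5%.
- q = 5% in both arms: 45.1 × 0.95 − 57.6 × 0.95 = −11.9 points. SE = 0.04195, and Φ(0.00625/0.04195 − 1.96) = 3.5%.
- q = 10% in both arms: −12.5 × 0.90 = −11.25 points. SE = 0.04187, and Φ(0.0125/0.04187 − 1.96) = 4.8%.

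These are two-proportion approximations at the ATP-5 size. The primary analysis itself is a linear regression with multiple imputation on all randomized subjects.

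**The case against.** The strongest reply is that the SAP does what the protocol says. Criterion 4 is open-ended in both documents, and its note deals with antibiotics after Day 5 and exempts only unrelated non-respiratory illness. The visit analyses in Protocol 11.4.2 (item 11) and SAP 8.2.10 use the same open phrase. On that view, late relapse counts as failure by design. This stands in part: the open window originates in criterion 4, and a reader who inferred that the SAP algorithm departs from the primary definition would be wrong. But it leaves an endpoint defined at Day 5 with a component running to about Day 30, beside other passages that close the same kind of event at Day 5 or Day 11.

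A second reply is that a visit-specific reading is natural. The rule's labels name D5V, and Protocol 7.3.2 has staff look for these events before and at Visit 3. The visit form is not in the documents, so a programmer may well filter by date. True, but the SAP does not say so.

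Three stronger inferences are not supported:

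- That all three visits always carry the same flag. This holds only for a subject with a qualifying visit. With no form submitted, the flag is absent or missing according to completion of each visit.
- That the Day 28 analysis is compromised. It is the last visit, so an undated rule gives essentially the intended result.
- That the recorded rate must fall below 57.6%, or that a 10% against 5% imbalance is spurious. The 57.6% comes from a blinded interim look after about 210 subjects had completed or terminated, and may already include late failures. More late rescue on placebo would be a real later difference, and it works against non-inferiority.

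**Conclusion.** The point holds for the Day 5 and Day 11 Visits. Criterion 4 and the rules in SAP 6.5.1.4 and 6.5.2.3 have no upper date limit. Followed as written, an LRTI-antibiotic visit after the Day 5 Visit makes a subject a D5V failure, and one after the Day 11 Visit makes a subject a D11V failure. That is at odds with the Day 5 hypothesis, with the outcomes limited to Days 5 and 11, and with the antibiotic count in the same DOOR score.

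The size is unknown. The figures above rest wholly on assumed late-visit rates of 0 to 10% and on 57.6% being free of late events. With equal rates nothing shifts when the arms are truly equal, but a true difference is diluted, which is anti-conservative. With unequal rates the estimate moves in a direction that cannot be foreseen. The documents do not show that the trial fails to measure Day 5 improvement, only that the stated rule would allow later events to decide it.

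**What to change.** Reconcile criterion 4 (Protocol 3.2.1, SAP 3.3.2, and the Day 11 counterpart) with the SAP rules:

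- Count a qualifying visit or hospitalization only if it is dated after randomization and on or before the study day of the visit analysed (D5V or D11V). Use the actual study day, since D5V may fall on Days 5 to 8. If the visit was missed or out of window, use the planned study day, as SAP 3.3.1 already does.
- Keep the existing *missing* branch when the visit was not completed and no qualifying event falls in the window. A blanket default to *absent* would turn missing data into passes.
- Apply the same limit to the visit and hospitalization terms of the D5V and D11V ordinal outcome in SAP 6.5.4.
- Correct MAVBRX to MAVABRX in the *absent* branch, and state that any form meeting *present* overrides forms meeting *absent*.

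The programming cost is small; Listing 19 shows that visit dates are held. The real cost is that this amends the wording of a primary-endpoint criterion, so it must be made before unblinding, and that late LRTI relapses will then count only at the later visits.

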6.5.2. Clinical Improvement at D11V and D28V

Clinical improvement at D11V is defined as fulfillment of all the following 1) For subjects who qualified based on the presence of at least two symptoms, then improvement must be observed in at least two symptoms present at enrollment (i.e., cough, sputum production, chest pain, difficulty breathing, or fever). For subjects who qualified based on the presence of one symptom and at least one vital sign abnormality, improvement must be observed in the one symptom present at enrollment 2) Absence of deterioration in any qualifying symptom (i.e., cough, sputum production, chest pain, difficulty breathing, or fever); or new vital sign abnormality not present at enrollment 3) No medically attended visit to an ambulatory medical facility (e.g., ED, outpatient clinic, urgent care center) or hospitalization for persistent or worsening LRTI at any time after randomization. Persistent or worsening LRTI is defined as receipt of a non-study antibiotic [parenteral or oral] treatment for LRTI or its complication. However, receipt of a non-study antibiotic after study day 11 will not be regarded as satisfying this definition for D11V if it is related to a new non-respiratory process that is unrelated to the prior diagnosis of LRTI.

Subjects will be assessed on whether they were enrolled based on at least two qualifying symptoms (cough, sputum production, chest pain, or difficulty breathing) or based on one qualifying symptom and one abnormal vital sign. Severity recorded on the LRTI Symptoms and Fever form (LRT) for Visit 1 will be used as baseline. Symptoms severity for D11V will be obtained from the solicited events form (LRS) for the event date corresponding to the date of study day 11. Symptoms severity for D28V will be obtained from LRT form for Visit 5. Vital signs were not recorded for D11V and D28V.

6.5.2.1. Improvement in Two Symptoms or One Symptom Present at Enrollment at D11V and D28V

For subjects who qualified based on two symptoms, improvement in symptoms at D11V or D28V will be defined as presence of at least one-step improvement in two qualifying symptoms present at enrollment. For subjects who qualified based on one symptom and one vital sign abnormality, clinical improvement at D11V or D28V will be defined as the presence of at least one-step improvement in the one symptom present at baseline. If the one qualifying symptom at baseline has a missing value at D11V or D28V, then improvement in symptoms at D11V or D28V is missing, respectively.

Improvement in fever at D11V or D28V is defined as changing from presence of fever at baseline to absence of fever on D11V or D28V, respectively. Fever will be present at D11V if temperature reported on the LRS form for study day 11 is $\geq 100.0^{\circ}\text{F}$ or if subjective fever is recorded on the LRS form on study day 11. A subject has fever at baseline or at D28V if the subject had subjective fever or a temperature of $\geq 100.0^{\circ}\text{F}$ reported on the LRT form (i.e. LRTTMPF ≥ 100 or LRTFEVYN = Yes) for Visit 1 or Visit 5, respectively. If

at least some of the temperature information is available at D11V or D28V, but none of it indicates objective or subjective fever, then fever is absent at D11V or D28V respectively. If none of the temperature or fever information is available at D11V or D28V, then fever is missing at D11V or D28V, respectively.

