### **7.3.3 Visit #4 (Day 11 + 3 days)**

Study subjects will be evaluated on Day 11 via telephone. Secondary and exploratory outcome measures will be assessed at this follow up. Study staff will complete the following procedures:

- Assessment of clinical improvement including:
  - Review and collection of temperature
  - Assessment and grading of LRTI symptoms
  - Occurrence of any medically attended visits
  - Receipt of any non-study systemic antibiotics
- Review of the subject's memory aid
- Assess and record any solicited events and UADEs

If the subject develops signs or symptoms of pneumonia (including fever, increased work of breathing, or increased/worsening cough) or develops a severe solicited event, the subject will be referred to his/her primary care provider or local urgent care center/ED. Study staff will assist in facilitating the follow up appointment. The study staff will share all pertinent information related to the study with the treating clinician including treatment arm assignment if clinically indicated as determined by the treating clinician and the study's site investigator.

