3.3. Study Definitions and Derived Variables

3.3.1. Timepoints

Day 5 Visit (D5V) represents Visit 3 which can occur any time from Day 5 to Day 8.

Day 11 Visit (D11V) represents Visit 4 which can occur any time from Day 11 to Day 14.

Day 28 Visit (D28V) represents Visit 5 which can occur any time from Day 26 to Day 30.

Day 1 is defined as the date of dose 1 for subjects treated with study product. For subjects not treated with study product, Day 1 will use their randomization date. The enrollment date will be used to define Day 1 for non-randomized subjects with PCT > 0.25 ng/mL. There is no Day 0 for this study, and the day preceding Day 1 will be reported as Day -1.

Study Day is defined relative to Day 1. If a visit did not occur, then study day will be imputed as its planned study day. Moreover, if a visit occurs out of the protocol defined window, then that visit will be treated as missing and its study day imputed as the planned study day in the Intention-to-Treat (ITT) analysis. Note that planned study day is 5 for D5V, 11 for D11V, and 28 for D28V.

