3.3.3. Clinical Improvement at D11V

Clinical improvement at D11V is defined as fulfillment of **all** the following criteria:

- For subjects who qualified based on the presence of at least two symptoms, then improvement must be observed in at least two symptoms present at enrollment (i.e., cough, sputum production, chest pain, difficulty breathing, or fever). For subjects who qualified based on the presence of one symptom and at least one vital sign abnormality, improvement must be observed in the one symptom present at enrollment. For symptoms other than fever, at least a one-step improvement (e.g., improvement from moderate to mild cough) will be considered a clinical improvement.
- **Note:** fever will be objectively (≥37.8 °C or 100.0 °F, measured anywhere on the body) or subjectively reported by the subject for the day preceding or on the D11V. For Day 11, fever will be

used similar to what has been done for Day 5 outcome measure definition i.e. clinical improvement requires absence of fever in the day preceding or at the D11V.

- **Note:** vital signs were not recorded at Days 11 and 28. Therefore, the subcomponents of clinical improvement at D11V and D28V are different from the subcomponents of clinical improvement used for the primary outcome measure at D5V (i.e., subcomponents at D11V and D28V do not include any reference to vital signs measures).
- Absence of deterioration in any qualifying symptom (i.e., cough, sputum production, chest pain, difficulty breathing, or fever). For symptoms other than fever, at least a one-step deterioration (e.g. worsening from mild to moderate cough) will be considered clinical deterioration.
- No medically attended visit to an ambulatory medical facility (e.g., ED, outpatient clinic, urgent care center) or hospitalization for persistent or worsening LRTI at any time after randomization (persistent or worsening LRTI is defined as receipt of a non-study antibiotic [parenteral or oral] treatment for LRTI or its complication). **Note:** receipt of a non-study antibiotic after study day 11 will not be regarded as satisfying this definition if it is related to a new non-respiratory process that is unrelated to the prior diagnosis of LRTI.

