6.4. Covariates and Subgroups

Subjects will be recruited from multiple clinical sites, and randomization will be stratified by site. No subgroup analyses will be performed. Study day of D5V and treatment indicator will be included as covariates in the linear regression model for clinical improvement at D5V. Similarly, study day of D11V and study day of D28V will be included as covariates in the linear regression model for clinical improvement for D11V and D28V, respectively. Covariates to be included in the multiple imputation models are listed in Section 8.4.

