6.5.1. Clinical Improvement at D5V

Clinical improvement at D5V is defined as fulfillment of all the following 1) Improvement in at least two symptoms present at enrollment (i.e., cough, sputum production, chest pain, or difficulty breathing) or one symptom and at least one vital sign abnormality present at enrollment 2) Absence of deterioration in any qualifying symptom (i.e., cough, sputum production, chest pain, or difficulty breathing); or new vital sign abnormality not present at enrollment 3) Absence of fever in the day preceding or at the D5V 4) No medically attended visit to an ambulatory medical facility (e.g., ED, outpatient clinic, urgent care center) or hospitalization for persistent or worsening LRTI at any time after randomization. Persistent or worsening LRTI is defined as receipt of a non-study antibiotic [parenteral or oral] treatment for LRTI or its complication. However, receipt of a non-study antibiotic after study day 5 will not be regarded as satisfying this definition if it is related to a new non-respiratory process that is unrelated to the prior diagnosis of LRTI.

Subjects will be assessed on whether they were enrolled based on at least two qualifying symptoms (cough, sputum production, chest pain, or difficulty breathing) or based on one qualifying symptom and one abnormal vital sign. Severity recorded on the LRTI Symptoms and Fever form (LRT) for Visit 1 will be used as baseline. Vital signs results recorded on the Vital Signs form (VS1) for Visit 1 and Visit 3 will be used to

derive normal or abnormal results for temperature, pulse, and respiratory rate for baseline and D5V, respectively. Symptoms severity for D5V will be obtained from the Solicited Events form (LRS) for the event date corresponding to the Visit 3 date from the Visit Documentation form (VD4). Normal values for the vital signs are:

- temperature ($<37.8^{\circ}\text{C}$ or 100.0°F),
- pulse (<90 bpm),
- respiratory rate (≤ 20 breaths per minute),

6.5.1.1. Improvement in Two Symptoms or One Symptom and One Vital Sign Present at Enrollment at D5V

For symptoms, clinical improvement at D5V will be defined as presence of at least one-step improvement in two qualifying symptoms present at enrollment. For subjects who qualified based on one symptom and one vital sign, normalization of the presenting abnormal vital sign and at least one-step improvement in the symptom will be considered a clinical improvement.

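### The Day 11 outcome is read on study day 11, but its window, covariate and antibiotic-day count follow the Visit 4 date (Days 11 to 14), and its fever rule contradicts the SAP's own definition

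*SAP*

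**What the plan says.** **What the visit is.** SAP 3.3.1: "Day 11 Visit (D11V) represents Visit 4 which can occur any time from Day 11 to Day 14". Protocol 7.3.3 makes it a telephone call whose tasks include "Assessment and grading of LRTI symptoms", collecting temperature and reviewing the memory aid. Protocol 11.4.2, item 2, sets the Day 11 non-inferiority analysis on clinical improvement at Visit 4.

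**Where the outcome is read.** SAP 6.5.2: "Symptoms severity for D11V will be obtained from the solicited events form (LRS) for the event date corresponding to the date of study day 11". SAP 6.5.2.2: "If at least one observed symptom deteriorated at study day 11, then there is no absence of deterioration at D11V". SAP 6.5.2.1: "Fever will be present at D11V if temperature reported on the LRS form for study day 11 is" 100.0°F or higher, or if subjective fever is entered on that form for that day. SAP 6.5.3 also stops the most severe solicited event at study day 11.

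**What follows the visit date.** SAP 6.4: "study day of D11V and study day of D28V will be included as covariates in the linear regression model for clinical improvement". SAP 3.3.1 treats an out-of-window visit as missing in the ITT analysis and sets its study day to the planned day. SAP 6.3 excludes such a subject from ATP-11. SAP 6.5.5 counts antibiotic days through the D11V study day. The footnotes to Tables 23 and 24 say the reported rates are for a visit day of 11.

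**How fever is defined.** SAP 3.3.3 takes fever measured, or "subjectively reported by the subject for the day preceding or on the D11V".

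**The other two timepoints.** At D5V, SAP 6.5.1 takes the LRS row "for the event date corresponding to the Visit 3 date from the Visit Documentation form (VD4"). At D28V, SAP 6.5.2 takes the Visit 5 LRT form.

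**The concern.** Of the three clinical-improvement outcomes, D11V is the only one whose symptoms are not tied to its visit, although its inclusion rule and its regression are. Four consequences follow.

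- For late calls, the model adjusts for a day on which the outcome was not read.
- Whether a Day 11 record counts depends on the date of a telephone call that the derivation does not otherwise use for symptoms.
- The fever component can be scored on a day outside its own definition.
- The Day 11 DOOR joins symptoms, fever and solicited events cut off at study day 11 to antibiotic days that run to the visit.

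At stake are the Day 11 non-inferiority analyses (ITT and ATP-11), which are secondary, and the exploratory analyses that use the D11V outcome, including the Day 11 DOOR.

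**Working it through.** The plan gives no figure to reproduce, so the check sets the rules side by side by day of the Visit 4 call.

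| Call on | Symptoms read on | Gap to covariate day | Fever days by SAP 3.3.3 | Fever day by SAP 6.5.2.1 | Shared fever day |
|---|---|---|---|---|---|
| Day 11 | 11 | 0 | 10, 11 | 11 | 11 |
| Day 12 | 11 | 1 | 11, 12 | 11 | 11 |
| Day 13 | 11 | 2 | 12, 13 | 11 | none |
| Day 14 | 11 | 3 | 13, 14 | 11 | none |

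The gap is call day minus 11. The defined fever days are call day minus 1 and call day.

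**Symptoms.** The dates agree only for a Day 11 call.

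**Fever.** The two rules never cover the same set of days. Even for a Day 11 call, the derivation ignores Day 10, which the definition includes. For Days 13 and 14 they share no day. SAP 8.3.8 and the DOOR imputation list in SAP 8.4.2 both use the visit-based fever window, so the SAP holds both versions.

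**Window.** Take a subject with a full study-day-11 LRS row and a call on Day 15. SAP 3.3.1 treats the visit as missing and sets its study day to 11. SAP 6.3 excludes the subject from ATP-11. The record that the derivation needs exists but is not used.

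**Antibiotic note.** SAP 6.5.2 exempts certain non-study antibiotics given after study day 11, while SAP 6.5.2.3 counts from the D11V study day. The same two dates compete here.

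**Share of calls affected.** The documents do not give the distribution of Visit 4 days. The range is 0% (all calls on Day 11) to 100% (none). An even spread over Days 11 to 14 would give 3/4 = 75%. That counts date mismatches, not changed outcomes.

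**Effect on the model.** This was examined by an illustrative simulation with assumed values: 560 subjects, 400 replicates, 75% improved at Day 11, calls on Days 11/12/13/14 in shares 40/25/20/15%, no treatment effect, and call day unrelated to arm. The model was improvement = intercept + treatment + (visit day − 11). Mean coefficients were:

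| Assumed rise per day | Visit-day coefficient, outcome read at visit | Visit-day coefficient, outcome read on Day 11 | Treatment coefficient, at visit / on Day 11 |
|---|---|---|---|
| 0.02 | 0.0198 | −0.0002 | −0.0035 / −0.0042 |
| 0.04 | 0.0410 | 0.0007 | 0.0000 / 0.0001 |

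Read at the visit, the covariate recovers the daily change. Read on Day 11, it has nothing to adjust for. The treatment coefficient is zero by construction, and the two readings differ by at most 0.0007 (0.0042 − 0.0035). The intercepts also agree (0.7526 against 0.7530, and 0.7490 against 0.7494). Under these assumptions the mismatch biases neither the difference nor the rates.

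**The case against.** The strongest reply is that a fixed study-day-11 reading is a deliberate convention. Fever, deterioration, the most severe solicited event (SAP 6.5.3) and the solicited-event terms in the DOOR imputation model (SAP 8.4.2) all stop at study day 11, and the objectives speak of efficacy on Day 11. SAP 9.3.1 says solicited events were recorded for Days 1 to 11, so later LRS rows may not exist. This stands as far as it goes: symptoms are not a lone slip, and a fixed Day 11 outcome would be legitimate. But then the visit window, the covariate, the table footnotes and the fever definition are the parts that do not fit. The SAP gives no such reason, and Protocol 8.1 runs the memory aid through Visit 4.

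A reader might infer that the grading done at Visit 4 is thrown away. The documents do not establish this. Staff review the memory aid at that call for gaps and discrepancies and record the data, so the call may be how the Day 11 row is completed. The SAP names LRT forms for Visits 1, 3 and 5 but none for Visit 4. For the same reason, not every subject without a diary entry for Day 11 need end up missing, and a qualifying medical visit might still settle failure.

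A reader might also infer that scoring a subject as improved on Day 11 who worsens on Day 12 is an error. Under a fixed Day 11 outcome that is a choice of timepoint.

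**Conclusion.** The inconsistency stands. The D11V clinical components are read on study day 11, while the definition of D11V, the protocol's analysis, the window, the covariate and the antibiotic-day count follow Visit 4. The fever derivation contradicts SAP 3.3.3. This is more than missing detail, because the stated rules can turn an observed Day 11 record into a missing outcome and can score fever on a day outside its defined window.

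The size is unknown: 0% to 100% of calls may fall after Day 11. It would be tempting to conclude that the Day 11 comparison of arms is biased. The documents do not support that, and the illustration shows no bias when visit day is unrelated to arm. The illustration does not model missing records or a call day that depends on how the subject is doing. The Day 5 primary analysis is untouched, and SAP 8.1.1 rests the non-inferiority conclusion on it alone.

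**What to change.** Use one date for every D11V component. The preferred version, matching the protocol and the D5V rule, is:

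- Take symptoms and deterioration from the record for the actual Visit 4 date, and fever from that date and the day before. Use whichever form captured the Visit 4 grading; the sponsor should confirm which one.
- Reconcile Protocol 8.1 (memory aid through Visit 4) with SAP 9.3.1 (Days 1 to 11), since this decides whether rows for Days 12 to 14 exist.
- Give the solicited-event cut-off (SAP 6.5.3 and 8.4.2) and the antibiotic-day cut-off (SAP 6.5.5) the same end date for the Day 11 DOOR.
- Keep the visit-day covariate, which then describes the day of measurement, and run the study-day-11 version as a sensitivity analysis.

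Moving symptoms alone would not do, because fever would stay on another date. If grades dated to Visit 4 do not exist, define the outcome as study day 11, drop the Visit 4 window and the visit-day covariate for it, and correct SAP 3.3.3 and the footnotes to Tables 23 and 24.

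The cost is SAP wording and a date key in the derivation program. Neither version calls for new data collection, but the preferred one is feasible only if Visit 4-dated grades were recorded.
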